### 2.1 Risk / Benefit Assessment

**Risk:** Inhaled n-acetylcysteine (NAC) is approved for the treatment of mucus associated airway disease, including asthma. The main side effect from inhaled n-acetylcysteine (NAC) is bronchospasm. We find that co-administering NAC and albuterol effectively prevents excessive bronchoconstriction in asthmatic patients. Specifically, in eight asthmatics that were given doses of 20% NAC as high as 3 mL together with 3 mL of albuterol, the largest FEV1 decline was 6%.

**Benefit:** Mucus plugs cause airway obstruction and symptoms of dyspnea. The role of mucolytics in decreasing plugs and increasing FEV1 has not been well studied. Our preliminary data, utilizing CT imaging and a novel scoring system, can identify and target a

subgroup of patients who may benefit from inhaled mucolytic treatment more so than the asthmatic population as a whole.

To minimize risk, study participants will be administered the first two treatments under the supervision of the study team in the Airway Clinical Research Center and will only be eligible to remain in the study if their post-treatment FEV1s are greater than 80% of their pre-treatment, pre-bronchodilator FEV1.

### **3 STUDY OBJECTIVES**

#### **3.1 Primary Objective**

The primary objective is to determine if inhaled NAC decreases mucus plugs and improves lung function in patients with asthma.

#### **3.2 Secondary Objectives**

The secondary objective is to determine the duration of benefit of inhaled NAC in asthma and identify characteristics of those subjects who benefit from mucolytic treatment.

### **4 STUDY DESIGN**

#### **4.1 Study Overview**

This is a multi-center, double-blind, randomized, 2 period crossover trial in 36 subjects with asthma who demonstrate mucus plugging on a screening CT lung scan. Screening data will be reviewed to determine participant eligibility. Participants who meet all inclusion criteria will self-administer nebulized 10% NAC (3 mL) and 2.5 mg albuterol inhalation solution (0.5 mL) or 0.9% saline (3 mL) and 2.5 mg albuterol inhalation solution (0.5 mL) to be taken 2 times per day for 14 days. Following an 8-week washout period, participants will be switched to the alternate group for 14 days of treatment. Participants will be assigned to the treatments in random order. Evaluations will be taken at baseline, end of first treatment, start of second treatment period, and at the end of the second treatment period.

The following treatment regimens will be used:

- Experimental treatment of 3.0 mL 10% NAC + 2.5mg/0.5 mL albuterol
- Placebo treatment of 0.9% saline + 2.5mg/0.5 mL albuterol

Total duration of participation will be 16 weeks. Total duration of the study is expected to be 2 years.

### **5 CRITERIA FOR EVALUATION**

#### **5.1 Primary Efficacy Endpoint**

FEV1 will be the primary endpoint because it is the most robust measure of airflow obstruction in asthma. We will compare the post-treatment FEV1s to pre-treatment baseline values. We calculate that with a sample size of 36 we will have 90% power to detect an

effect size of 5% improvement in FEV1 and a within patient correlation for repeated measures of FEV1 of 0.9.

## 5.2 Secondary Efficacy Endpoints

We intend to examine the effect of the treatment on CT mucus score, however, because the CT mucus score is a novel measurement, we do not have preliminary data to describe the natural history of mucus in the airway over time or with treatment. Therefore, for the purpose of this study, we intend to describe any changes we observe.

Other Secondary efficacy endpoints will include:

- FVC
- PEF (AM and PM)
- Air trapping (RV/TLC ratio)
- FeNO
- Blood eosinophils

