### **8.1.14 CT Imaging of the Thorax**

A single inspiratory low dose CT scan of the thorax using a model based iterative reconstruction (MBIR) approach will be taken at visits 3, 6, 7, and 10.

The risks associated with CT scanning are that of the additional amount of radiation exposure. At the UCSF, the additional amount of radiation that each participant will receive as a result of participating in this study will be approximately 5 mSv, which is slightly greater than the yearly natural background of radiation in the US, which is 3mSv. This amount of radiation may involve a low risk of cancer. A participant should not participate in this study if she is pregnant or breastfeeding.

Additional risks are associated with the uncovering abnormal findings. There is a risk of possible detection of an abnormality in the lung which, after testing or treatment, is found not to be disease-causing. This includes possible misdiagnosis of lung cancer. Such findings may result in unnecessary anxiety for the participant, and increase his or her chance that an outpatient physician may believe that the abnormality is lung cancer and order further testing. This testing could include additional CT scans with additional radiation exposure, other types of scans to determine if the abnormalities are rapidly growing, a needle biopsy (taking a sample of the abnormality with a needle) or a lung biopsy which requires surgery. Whether these additional studies would be performed would be a decision that the participant would make with his/her regular physician.

In an effort to minimize risk to participants, scans will be read by radiologists that have expertise in interpreting findings of chest CTs. If there are any abnormalities, other than those that are usually found in asthmatic patients, observed by the clinical center radiologists, these will be reported to the principal investigator, who will in turn communicate these findings to the participant. The most likely abnormal result will be the identification of a spot on the lung that might be cancer.

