#### **9.5 Visit 4 (Day 7)**

1. Review and record changes to concomitant medications.
2. Perform and record vital signs.
3. Perform and record oximetry.
4. Perform and record urine pregnancy test
5. Perform and record fractional exhaled nitric oxide (FeNO) measurement.
6. Perform and record spirometry.
7. Perform and record post-bronchodilator reversibility.
8. Perform and record plethysmography with bronchodilation.
9. Randomize
10. Provide education on use of personal nebulizer and administration of study medication.
11. Administer first two treatments of study drug treatment, spaced 4-6 hours. FEV1 measurements should be taken before and after each treatment.
12. Dispense study drug and initiate study diary if subject's post-treatment FEV1 is greater than 80% of pre-treatment FEV1.
13. Schedule participant for phone follow-up in 3-5 days and visit 5 in 7 days.

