### 14.3 Analysis of Primary Endpoint

The primary analysis is a paired t-test analysis of the % change in FEV1 from the start to the end of the two-week treatment period with two times daily NAC (Mucomyst-10). The secondary analysis will be to determine how the change in FEV1 relates to the change in CT mucus score.

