### 14.6 Sample Size

We propose a sample size of 36, which will provide us with the power to examine the effect of NAC in a subgroup of individuals with asthma who have CT evidence of intraluminal mucus and to identify the CT mucus score that performs best as a biomarker of treatment response to NAC. Participants will be enrolled if their CT mucus scores are  $\geq 5.0$ . The sample size is obtained when we factor in an effect size of 5% improvement in FEV1, a standard deviation for change in FEV1 of 20%, a within patient correlation for repeated measures of FEV1 of 0.9, and a power of 90%.

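### The Visit 3 CT both applies the entry threshold and is the only period 1 baseline, so a described fall in mucus score from Visit 3 would include regression to the mean

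*Combined protocol and SAP*

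**What the plan says.** Section 4.1 enrols patients who "demonstrate mucus plugging on a screening CT lung scan". Section 14.6 sets the cut-off: "Participants will be enrolled if their CT mucus scores are" at least 5, as does the inclusion list in Section 6.2.

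Section 8.1.14 states that CT scans "will be taken at visits 3, 6, 7, and 10". The visit lists in Section 9 and Appendices A and B agree. Visit 3 is Day 0. Randomisation is at Visit 4 (Day 7), where staff "Administer first two treatments of study drug treatment, spaced 4-6 hours".

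For the CT score as an endpoint, Section 5.2 notes that there are no preliminary data on how mucus behaves over time or with treatment, and concludes: "for the purpose of this study, we intend to describe any changes we observe". Section 14.3 adds: "The secondary analysis will be to determine how the change in FEV1 relates to the change in CT mucus score". No NAC-versus-placebo contrast for the CT score is written down. Reducing mucus plugs is nevertheless part of the primary objective (Section 3.1). Duration of benefit is a secondary objective (Section 3.2) without a stated analysis.

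**The concern.** Patients picked because one reading was high tend to read lower next time, treated or not. This happens whenever the score varies between scans, through reading error or natural fluctuation. If the reading that selected them is also the before value, that fall is counted as change.

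Here the period 1 change (Visit 3 to Visit 6) starts from a selected value, and the period 2 change (Visit 7 to Visit 10) does not. A plan that only describes changes gives the reader no way to separate mucus clearance from this artefact. At stake is how the trial reports the mucus part of its primary objective. The analysis of FEV1 change against CT change would also pool changes measured from two kinds of baseline.

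**Working it through.** **1. Is Visit 3 the selecting scan?** The protocol never says in words which scan applies the cut-off. Section 4.1 calls it a screening CT; Visit 3 is the only scheduled CT before randomisation at Visit 4. A prior radiologist-read CT appears only in the criterion on post-bronchodilator FEV1, not as the source of the score. The double role of Visit 3 is therefore an inference from the schedule. If an older scan applied the cut-off instead, most or all of the artefact would fall before Visit 3.

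**2. Plan's own figure.** There is none for the CT score: no scale, standard deviation or repeatability. The 36 participants are sized on FEV1 and do not depend on this point.

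**3. Formula.** For two scans with equal mean and SD σ and correlation ρ, selecting on the first gives an expected untreated fall of (1 − ρ) × σ × φ(z)/f, where f is the fraction above the cut-off and z its normal quantile.

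**4. Inputs.** Section 1.1 reports that 58% of the severe-asthma cohort have at least one plugged segment and 27% more than four. Assume a latent normal score, rounded to whole segments:

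- f = 0.27, so z = 0.613 and φ(z)/f = 1.22.
- The 42% with score 0 lie below 0.5 (z = −0.202) and the 27% lie above 4.5. So σ = (4.5 − 0.5)/(0.613 + 0.202) = 4.91.
- The latent mean is 4.5 − 0.613 × 4.91 = 1.49. The mean after selection is 1.49 + 4.91 × 1.2246 = 7.50.
- Fall = 6.01 × (1 − ρ).

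**5. Results with no drug effect.** The simulation used four scans per patient, scores rounded and limited to 0–20 (an assumed range), the same ρ between every pair of scans, selection on the first scan only, and equal sequences. The mean Visit 3 score was 7.52.

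| Assumed latent ρ | Correlation of rounded scores | Fall by formula | Visit 6 − Visit 3 | Visit 10 − Visit 7 | Pooled change on NAC | Pooled change on placebo | NAC − placebo |
|---|---|---|---|---|---|---|---|
| 0.95 | 0.93 | 0.30 | −0.32 | 0.00 | −0.16 | −0.16 | 0.00 |
| 0.9 | 0.87 | 0.60 | −0.62 | 0.00 | −0.31 | −0.31 | 0.00 |
| 0.8 | 0.76 | 1.20 | −1.17 | 0.01 | −0.59 | −0.58 | −0.01 |
| 0.7 | 0.65 | 1.80 | −1.71 | 0.00 | −0.86 | −0.86 | 0.00 |
| 0.5 | 0.45 | 3.01 | −2.68 | 0.01 | −1.33 | −1.34 | 0.00 |

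The formula and simulation differ at low ρ because scores cannot go below 0.

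**6. Sensitivity.**

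- With a heavier upper tail (exponential, mean excess 5, cap 20; selected mean about 9.3), the fall is 0.4, 0.7, 1.4 and 2.1 for latent ρ of 0.95, 0.9, 0.8 and 0.7.
- If the screened group is richer in plugs than the cohort, the artefact shrinks. For ρ from 0.95 to 0.5 it is 0.06–0.61 SD at f = 0.27, 0.05–0.48 SD at f = 0.40 and 0.03–0.34 SD at f = 0.58.

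**7. Unequal sequences.** In a change-score contrast the artefact acts as a period effect. With 22 patients in one sequence and 14 in the other, for example, an unadjusted paired difference in changes shifts by (22 − 14)/36 of the period 1 fall, about 0.07 to 0.6 points. Section 7.1 states 1:1 allocation without mentioning blocking, and Section 11.3 replaces withdrawals, so final sequence sizes may differ.

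**8. FEV1 change against CT change.** This was reasoned, not computed. If the extra period 1 fall is reading error, FEV1 has no matching movement and the association is mainly diluted. If it is real fluctuation in mucus, FEV1 may move with it, but not because of treatment.

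**The case against.** The trial is randomised, placebo-controlled and crossover. Patients in both sequences regress alike from Visit 3, so describing changes in both arms would show the same fall on placebo. Section 5.2 states an intent to examine the effect of treatment, the CT score is a secondary endpoint that is expressly descriptive, and Section 14 promises a fuller SAP. All of this stands, and the last columns of the table confirm that the balanced contrast is centred on zero.

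Three stronger readings are tempting, and the documents do not support them.

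- A reader might infer that the plan would make an inert drug look effective. That requires ignoring the placebo arm, which no section proposes.
- A reader might infer that a lower score at Visit 7 than at Visit 3 will be reported as lasting benefit. Section 3.2 names no visit, variable or comparator, so this comparison is not a stated analysis. The warning applies only if someone makes it.
- A reader might infer that the artefact creates a false association between FEV1 and CT change. As reasoned above, added noise is the more likely result.

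The objection leaves one thing untouched: the sound contrast is available but not specified, and what is specified is description of change from a baseline chosen for being high.

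**Conclusion.** The point holds in a limited form. Described within-group falls from Visit 3 would overstate mucus clearance, equally in both sequences. The size cannot be obtained from the documents. The illustrations give 0.3 to 2.7 points on a Visit 3 mean of about 7.5, for assumed correlations of 0.95 to 0.5, and the artefact goes to zero as repeatability approaches 1. They rest on an assumed score distribution and range, on one constant correlation between scans, and on Visit 3 being the selecting scan. The balanced randomised CT contrast and the FEV1 primary endpoint are not biased by it. The plan should still be changed, because mucus clearance is part of the primary objective and the better analysis uses scans already scheduled.

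**What to change.** Amend Sections 5.2 and 14.3, and carry the same wording into the later SAP:

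1. Define the CT mucus score effect as the within-patient NAC-minus-placebo difference in end-of-treatment scores (Visits 6 and 10), adjusted for period. The period term guards against unequal sequence sizes and against Visits 6 and 10 having regressed by different amounts. Label within-group changes from Visit 3 as subject to regression to the mean and not evidence of effect.
2. If CT is used for duration of benefit, compare Visit 7 scores between the NAC-first and placebo-first sequences, adjusted for the Visit 3 score, and not Visit 7 with Visit 3.
3. Relate FEV1 to CT score using NAC-minus-placebo differences in each.

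It would also help to state that the Visit 3 scan applies the cut-off, if that is so.

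The cost is wording only, with no added scans, visits or participants. Reported within-arm falls may look less favourable. The Visit 7 comparison is between about 18 patients per sequence (36/2), so it will be imprecise. The end-of-treatment contrast relies on negligible carryover, as the FEV1 crossover analysis already does.

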## 5.3 Safety Evaluations

All participants will have their first two doses of each treatment period administered in the clinic under the supervision of a study nurse or study clinician. Participants will receive instruction on nebulizer use utilizing a teach-back method to ensure comprehension. Participants who are unable to successfully teach back nebulizer setup or drug self-administration will be excluded from continued participation.

Additionally, while acute anaphylactoid reactions have only been observed in the setting of IV administered NAC, each participant will be observed for the first two treatments, lasting approximately 6 hours, by a study nurse or study clinician.

All participants will be asked to complete a log of study drug administration and any subjective side effects.

Additionally, participants will have access via pager to a study nurse or clinician 24 hours a day, 7 days a week.

Interim safety evaluations will be done after 7 days of treatment during each treatment period. Additional safety evaluations will also be done if anticipated adverse events exceed frequencies documented in the literature, unanticipated adverse events occur, or rare but serious adverse events occur. Definitions of these terms and details of our safety evaluation plan are described in section 14.

## 6 PARTICIPANT SELECTION

### 6.1 Study Population

Participants with a diagnosis of asthma who meet the inclusion and exclusion criteria will be eligible for participation in this study.

### 6.2 Inclusion Criteria

1. Male or female between the ages of 18 and 80 years of age at Visit 1

2. Written informed consent obtained from subject and ability for subject to comply with the requirements of the study.
3. Able to perform reproducible spirometry according to ATS criteria
4. Physiological evidence of airflow obstruction (FEV1 bronchodilator reversibility of  $\geq 12\%$  or hyperreactivity to methacholine reflected by a methacholine PC20  $\leq 16$  mg/mL) Historical methacholine data may be allowed. An exception will be made for enrollees whose FEV1 is  $< 50\%$  predicted (precluding methacholine challenge testing. If bronchodilator reversibility is  $< 12\%$  in these participants, a diagnosis of asthma acceptable to the investigator is sufficient for inclusion in ENACT.
4. Clinical history of asthma per patient report or medical record
5. Pre-bronchodilator FEV1  $> 35\%$  predicted
6. Post-bronchodilator FEV1  $> 40\%$  but  $< 90\%$  predicted. If the participant has past evidence of mucus impaction as described by a radiologist on a prior chest CT scan, then post-bronchodilator FEV1 needs to be  $> 40\%$  but  $< 95\%$  predicted.
7. Asthma requiring treatment with inhaled corticosteroids (ICS) for 3 months or greater.
8. CT mucus score  $\geq 5$
9. Ability to tolerate study drug reflected by a post-treatment FEV1  $\geq 80\%$  of pre-treatment, pre-bronchodilator FEV1

### 6.3 Exclusion Criteria

1. Pregnant, breastfeeding, or unwilling to practice birth control during participation in the study.
2. Presence of a condition or abnormality that in the opinion of the Investigator would compromise the safety of the patient or the quality of the data.
3. Smoking of tobacco or other recreational inhalants in last year and/or  $> 10$  pack-year smoking history
4. Current participation in an investigational drug trial
5. Uncontrolled asthma as evidenced by an asthma exacerbation in 6 weeks prior to study participation or albuterol use greater than 8 puffs per day
6. Other chronic pulmonary disorders, including (but not limited to) cystic fibrosis, chronic obstructive pulmonary disease, chronic bronchitis, vocal cord dysfunction (that is the sole cause of respiratory symptoms and at the PI's discretion), severe scoliosis or chest wall deformities that affect lung function, or congenital disorders of the lungs or airways
7. Unwillingness to follow study procedures
8. History of allergy or intolerance to study drug
9. Any other criteria that places the subject at unnecessary risk according to the judgment of the Principal Investigator

### 6.4 Concurrent Medications

All participants should be maintained on the same medications throughout the entire study period, as medically feasible, with no introduction of new chronic therapies.

## 6.5 Allowed Medications and Treatments

Standard therapy for asthma is allowed except for treatments noted in the exclusion criteria described above and as noted in the prohibited medications section below.

## 6.6 Prohibited Medications and Treatments

The following medications are prohibited during the study and administration will be considered a protocol violation.

- Thiols and thiol derivatives
- Activated charcoal
- Inhaled insulin

## 7 STUDY TREATMENTS

### 7.1 Method of Assigning Participants to Treatment Groups

Up to 36 eligible patients will be randomly assigned to receive either the experimental treatment (10% NAC) or the placebo treatment (0.9% saline) during period 1 in a 1:1 ratio using a SAS-based computer-generated randomization scheme accessed by the investigational pharmacist. The UCSF investigational pharmacist will complete a randomization worksheet and log the group assignment for subjects enrolled at both UCSF and UC Davis. The UCSF investigational pharmacist will contact the UC Davis pharmacist by email or phone to inform them of the randomization. The randomization log will be shared with investigators upon study completion or in the event of a serious safety concern.

### 7.2 Blinding

Due to the objectives of the study, the identity of experimental and placebo treatments will not be known to investigators, research staff, or patients. The following study procedures will be in place to ensure double-blind administration of study treatments.

Access to the randomization code will be strictly controlled.

Packaging and labeling of experimental and placebo treatments will be identical to maintain the blind.

The study blind will be broken on completion of the clinical study and after the study database has been locked.

During the study, the blind may be broken **only** in emergencies when knowledge of the patient's treatment group is necessary for further patient management. When possible, the Investigator should discuss the emergency with a Quality Assurance officer and a representative from the Committee on Human Research prior to unblinding. Should unblinding become necessary the Investigator will contact the investigational pharmacist directly.

### 7.3 Formulation of Test and Control Products

NAC (trade name: Mucomyst) is manufactured by American Regent. The active drug studied here is 10% NAC. It will be delivered via nebulizer.

### 7.3.1 Formulation of Test Product

10% NAC is an existing formulation of Mucomyst (Mucomyst-20), manufactured by American Regent, for aerosol administration in the management of patients with chronic bronchopulmonary disease. 10% NAC is a colorless solution that requires no reconstitution.

Albuterol sulfate inhalation solution is an existing formulation of Proventil Nebules, manufactured by Nephron Pharmaceuticals Corporation for oral inhalation in the management of patients with bronchospasm. Albuterol sulfate inhalation solution is a clear, colorless solution.

Table 1: Formulation and Measured pH of 10% NAC, control product and albuterol

	10% NAC	0.9% Saline	Albuterol
Active Ingredient, mg/mL	Acetylcysteine 100mg/mL		Albuterol sulfate 2.5 mg/0.5mL
Other ingredient, mg/mL	Edetate disodium, sodium hydroxide, purified water	Sodium chloride Purified water	Water, sodium chloride, sulfuric acid
pH	7	5.7	3-5

